All Screening laboratory results must be reviewed, signed and dated by the Investigator for review and signature prior to the randomization of a subject. Subjects will not be randomized into the study if laboratory or other Screening result abnormalities are deemed clinically significant by the Investigator.

When blood draws are performed as part of a clinic visit, the draws should be performed after all clinical assessments and completion of questionnaires and vital sign measurements, and before study drug administration. Urine samples will be obtained for macroscopic urinalysis (dipstick done at the central laboratory which will include specific gravity, pH, protein, glucose, ketones, blood and nitrites) and a microscopic urinalysis at Screening. For all other visits that require a urinalysis, the central laboratory will perform a urine dipstick analysis and if the results are abnormal, the central laboratory will perform a microscopic urinalysis.

If required by country regulatory authorities or considered warranted by the Investigator to confirm eligibility, subjects will be tested for antibodies to the Human

Immunodeficiency Virus (HIV) at Screening and documented that the test has been performed. This testing is to be done at a local lab. A subject will not be eligible for study participation if test results indicate a positive HIV infection. AbbVie will not receive results from the testing and not be made aware of any positive result.

A certified central laboratory will be utilized to process and provide results for the clinical laboratory tests. The central laboratory chosen for this study will provide instructions regarding the collection, processing and shipment of appropriate samples.

The laboratory results will be provided by the central laboratory to the investigative site where they will be reviewed, signed and dated by the Investigator and filed as source data. For any abnormal value outside of the reference range, the Investigator will indicate on the report if the result is clinically significant (CS) or not clinically significant (NCS). All abnormal laboratory test results that are considered clinically significant by the Investigator will be followed to a satisfactory resolution. Laboratory abnormalities are considered to be adverse events only if they result in discontinuation from the study, necessitate therapeutic medical intervention, and/or if the Investigator considers them to be an adverse event.

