5.5 Treatments

5.5.1 Treatments Administered

5.5.1.1 Adalimumab

Adalimumab will be administered in this study open-label and at the standard dosing regimen 40 mg sc eow except in one arm of Part 2 as described below.

- Subjects randomized to Arm 1/Part 1 or assigned to Arms 1 and 4 of Part 2 at Week 16 (as described in Section 5.1 and Table 2), will receive adalimumab 40 mg eow. Starting at the Baseline (Day 1) visit, subjects who are eligible for randomization will receive the first dose of study drug: adalimumab 40 mg/0.8 mL.
- Subjects assigned to Arm 2/Part 2 (as described in Section 5.1 and Table 2), will receive adalimumab 40 mg ew beginning at the Week 16 visit.
- Subjects entering the rescue arm at or after Week 24 will have adalimumab introduced or escalated at the Investigator's discretion. For the recommended rescue treatment regimens see Section 5.1 Overall Study Design and Plan: Description.

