The Safety population Part 2 consists of all subjects who received at least one dose of the Part 2 study medication. The data collected from Week 16 to Week 32 will be included and analyzed by "as treated" treatment groups that subjects received when entering in Part 2. The data collected after the initiation of the rescue medication will be summarized separately, and not be included in the analysis.

"As treated" treatment groups are defined as follows:

1. ADA 40 mg eow
2. ADA 40 mg ew + MTX 15 mg ew
3. MTX 20 - 25 mg or highest tolerable dose ew
4. ADA 40 mg eow + MTX 20 - 25 mg or highest tolerable dose ew

Rescue Population

The Rescue population consists of all subjects who received at least one dose of the rescue medication after Week 24 visit. The data collected after the initiation of the rescue medication will be summarized separately by the Part 2 treatment groups as well as overall.

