7.2 Analysis of Adverse Events

7.2.1 Treatment-Emergent Adverse Events

Treatment-emergent adverse events (TEAEs) will be defined based on the following:

- Part 1: TEAEs will be defined as any event with an onset date that is on or after the first dose of Part 1 study drug, and
 - no more than 70 days after the last dose of ADA and 30 days after the last dose of MTX, if the subject discontinued prematurely from Treatment Part 1 or did not enter the Part 2, or
 - prior to date of first dose of Part 2 study drug if the subject entered Part 2.

- Part 2: TEAEs will be defined as any event with an onset date that is on or after the first dose of Part 2 study drug and with an onset date no more than 70 days after the last dose of ADA or 30 days after the last dose of MTX.

Events where the onset date is the same as the study drug start date are assumed to be treatment-emergent, unless the study drug start time and the adverse event start time are collected and the adverse event start time is prior to the study drug start time. If an incomplete onset date was collected for an adverse event, the event will be assumed to be treatment emergent unless there is other evidence that confirms the event was not treatment-emergent (e.g., the event end date was prior to the study drug start date).

Adverse event data will be presented by SOCs and PTs using MedDRA Version 21.1 or most up to date version.

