7.3 Analysis of Laboratory Data

7.3.1 Analysis for Continuous Laboratory Data

Observed values of hematology, chemistry, and urinalysis variables which are measured longitudinally will be summarized by visits and by the two treatment groups in Part 1 and by the four treatment groups in Part 2. The following summary statistics of each visit will be presented for each treatment group: sample size, observed mean, standard deviation, minimum, median, and maximum.

Mean change and percent change from baseline in selected laboratory variables will be summarized by the two treatment groups in Part 1 and by the four treatment groups in Part 2 at each visit. Mean difference between the two treatment groups in Part 1 will be compared using one-way ANOVA with treatment as a factor. Mean difference and the associated 95% CIs will be presented at each visit. The selected laboratory variables of clinical interest include: Hematocrit, hemoglobin, Red Blood Cell (RBC) count, White Blood Cell (WBC) count, platelet count, lymphocytes, neutrophils, creatinine, Aspartate aminotransferase (AST), aminotransferase (ALT), Cholesterol, Glucose, Triglycerides.

The last evaluation prior to the first dose of study drug in Part 1 or Part 2 will be used as Baseline for Part 1 or Part 2, respectively.

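### At the Week 16 switch, the treatment-emergent rules in SAP 7.2.1 do not place every adverse event in exactly one Part

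*SAP*

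**What the plan says.** SAP 7.2.1 defines treatment-emergent events separately for the two Parts. For a subject who continues, Part 1 runs from the first Part 1 dose and takes events with onset "prior to date of first dose of Part 2 study drug if the subject entered Part 2". Part 2 takes "any event with an onset date that is on or after the first dose of Part 2 study drug", up to a limit after the last dose.

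Two general rules follow, and neither names a Part:

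- Same-day rule: "Events where the onset date is the same as the study drug start date are assumed to be treatment-emergent". The exception is an event whose start time is earlier than the drug start time, where both times are collected.
- Incomplete dates: "If an incomplete onset date was collected for an adverse event, the event will be assumed to be treatment emergent", unless other evidence shows otherwise. The example given is an event that ended before study drug began.

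On a visit day, Protocol 5.3.1.1 has blood drawn after clinical assessment, "completion of questionnaires and vital sign measurements, and before study drug administration". Protocol 5.1.2.2 has Part 2 drug dispensed at Week 16 for use at that visit or on the subject's usual MTX day. Under Protocol 5.5.1.1, Arm 2 subjects "will receive adalimumab 40 mg ew beginning at the Week 16 visit".

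The data windows in SAP 5.1 meet at the same visit. The Part 1 safety population uses data up to Week 16. For Part 2, "The data collected from Week 16 to Week 32 will be included". For laboratory change, SAP 7.3.1 says "The last evaluation prior to the first dose of study drug in Part 1 or Part 2 will be used as Baseline" for the corresponding Part.

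**The concern.** Week 16 is both the last Part 1 assessment and, for many subjects, the day of the first Part 2 dose. Three of the four Part 2 arms change regimen then: Arm 1 drops MTX, Arm 2 moves to weekly adalimumab and Arm 4 adds adalimumab. Only Arm 3 carries on unchanged.

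The Part 1 boundary is set by calendar date, while the order of procedures within that date puts assessment before dosing. A finding from the pre-dose assessments, if its onset is dated that day, is tabulated under a regimen the subject had not yet started. For example, an event of MTX escalation dated to the Week 16 visit would appear under adalimumab plus MTX in Arm 4 and be missing from the randomised Part 1 safety comparison. What is at stake is correct attribution in the safety tables by Part. No efficacy analysis is involved.

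**Working it through.** The plan states no figure to reproduce, so the check applies the rules of SAP 7.2.1 to each possible case. Take a subject who entered Part 2, and let D be the date of the first Part 2 dose.

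| Onset of event | Part 1 | Part 2 |
|---|---|---|
| Before D | yes | no |
| On D, one or both times missing | no | yes |
| On D, both times known, event after dose | no | yes |
| On D, both times known, event before dose, exception applies to the Part 2 start | no | no |
| After D | no | yes |
| Incomplete date, could be either side of D, no other evidence | yes | yes |
| Incomplete date, event known to have ended before D | yes | no |

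Events fully dated before or after D split cleanly. The difficulties lie in three rows.

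1. **On D without both times.** The event is counted in Part 2 even if it was found before the dose. This is probably the usual same-day case. Protocol 6.1 asks for the date of onset and mentions no clock time, whereas Protocol 5.5.6 has dosing dates and times recorded in a diary.
2. **On D, timed before the dose.** Part 2 excludes the event by time and Part 1 has already excluded it by date. No sentence returns it to Part 1.
3. **Incomplete date.** The event is presumed emergent with no Part named. SAP 7.1 does not impute missing safety data, so no other rule chooses a Part.

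**Laboratory values.** SAP 7.3.3 counts subjects with CTC Grade 3 or higher values by Part. Under the windows in SAP 5.1, a pre-dose Week 16 value lies in both, so one such value can be counted in both summaries. SAP 7.3.1 meanwhile treats that value as Part 2 Baseline. The blood pressure, pulse and weight criteria in SAP 7.4 need a change from Baseline, so a value that is itself the Part 2 Baseline cannot meet them in Part 2.

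**What one misplaced subject does.** Inputs from SAP 4.4: 120 per arm, with MDA rates of 40% on adalimumab + MTX and 20% on escalated MTX. Arm size is 120 × proportion, and the shift is 100 / arm size.

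| Part 2 arm | Size | Shift per subject (points) | Subjects needed to exceed 5% |
|---|---|---|---|
| 1 | 120 × 0.40 = 48 | 100/48 = 2.1 | 3 |
| 2 | 120 × 0.60 = 72 | 100/72 = 1.4 | 4 |
| 3 | 120 × 0.20 = 24 | 100/24 = 4.2 | 2 |
| 4 | 120 × 0.80 = 96 | 100/96 = 1.0 | 5 |

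With 10% dropout (108 per arm) the sizes are about 43, 65, 22 and 86, and the shifts 2.3, 1.5, 4.6 and 1.2 points. In Part 1 one subject is 100/120 = 0.8 points. The 5% column refers to the frequent-event table in SAP 7.2.1.5. The largest shift is in Arm 3, the arm whose regimen does not change; in the other three arms it is 1.0 to 2.1 points before dropout.

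**The case against.** The best defence is that the SAP classifies by onset date and not by when an event is found. If times are not collected, the two definitions divide fully dated events without gap or overlap, and assigning day D to Part 2 is an ordinary convention. The same-day sentence also says only study drug, where the definitions name Part 1 or Part 2 drug. It may refer to the start of the whole study. On that reading the time exception concerns Day 1 alone and no event falls in neither Part.

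Much of this stands. The neither-Part case is conditional on times being collected and on how the exception is read. The first problem survives both readings, because the Part 1 boundary still excludes day D and the Part 2 definition still includes it. The incomplete-date rule still names no Part.

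Other protections limit the harm. Laboratory abnormalities are adverse events only under the conditions in Protocol 6.1.1.1. Relationship is assessed for both adalimumab and MTX (Protocol 6.1.3). Serious events, deaths and events leading to discontinuation of study drug are listed individually (SAP 7.2.2). The Arm 4 label includes MTX, so an MTX event there is not shown against adalimumab alone.

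A reader might infer three stronger things that the documents do not support:

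- That everything found at the Week 16 visit is charged to the new regimen. A complete, earlier onset date keeps an event in Part 1.
- That SAP 7.2.1 contradicts SAP 7.3.1. One sets an adverse event date convention and the other a baseline for laboratory change. They are inconsistent about the same sample, but they govern different outputs.
- That a fifth of Part 1 events move because Week 16 is one of five post-baseline Part 1 visits, or that the randomised arms are distorted to different degrees. Visits are not onset dates, and the documents give no adverse event rate from which to work out either effect.

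**Conclusion.** The point holds as a minor one. SAP 7.2.1 counts an event dated on the day of the first Part 2 dose under the new regimen even when it preceded that dose. It can drop such an event from both Parts if times are collected and the exception applies to the Part 2 start. It can count an event with an incomplete date in both. SAP 5.1 likewise allows one pre-dose Week 16 laboratory value into both Parts' Grade 3 or higher summaries.

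The number of events affected cannot be derived from the documents. The shift of about 1 to 4 points per misplaced subject assumes that the planned MDA rates hold and that all 120 per arm enter Part 2; with 10% dropout the upper end is 4.6 points. The consequence is limited to descriptive safety tables, and the primary and secondary efficacy analyses are untouched.

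**What to change.** In SAP 7.2.1, assign each event to exactly one Part:

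- End Part 1 at the first Part 2 dose by date and, where collected, time, so that a same-day event timed before the dose goes to Part 1.
- For untimed events on that date, keep in Part 1 those identified from the pre-dose Week 16 laboratory or vital-sign assessments. Assign the rest to Part 2 by default.
- For an incomplete onset date, choose the Part from the known portion of the date. Where that does not settle it, apply one stated default.

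In SAP 5.1, count Part 2 laboratory and vital-sign findings only from values after the first Part 2 dose, in line with the Part 2 Baseline in SAP 7.3.1 and 7.4.

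The cost is a few sentences and a small change to the treatment-emergent flag. The documents do not say that the adverse event form records how an event was found, so linking an event to the Week 16 sample may need a short data review. Untimed same-day events would still rest on a convention, but a stated one.

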7.2.1.1 Adverse Event Overview

The number and percentage of subjects experiencing TEAEs will be summarized for the following AE categories by the two treatment groups in Part 1 and by the four treatment groups in Part 2:

- All TEAEs
- Treatment-emergent serious adverse events (SAEs)
- Treatment-emergent severe adverse events
- TEAEs reasonably possibly related to study drug
- TEAEs leading to discontinuation of study drug
- TEAE leading to death

Additional AEs may be considered for tabulation/summary based on recommendations from Clinical and Safety as deemed appropriate.

7.2.1.2 Adverse Events by System Organ Class and Preferred Term

The number and percentage of subjects experiencing adverse events will be tabulated by SOC and MedDRA PT by the two treatment groups in Part 1 and by the four treatment groups in Part 2. The SOCs will be presented in alphabetical order, and the PTs will be presented in alphabetical order within each SOC.

Subjects reporting more than one adverse event for a given MedDRA preferred term will be counted only once for that term (most severe incident for the severity tables and most related incident for the relationship tables). Subjects reporting more than one type of adverse event within a SOC will be counted only once for that SOC. Subjects reporting more than one type of adverse event will be counted only once in the overall total.

7.2.1.3 TEAEs by Maximum Severity

TEAEs will also be summarized by maximum severity by the two treatment groups in Part 1 and by the four treatment groups in Part 2. If a subject has an AE with an unknown severity, then the subject will be counted in the severity category of unknown, even if the subject has another occurrence of the same event with a severity present. The only exception is that if the subject has another occurrence of the same AE with the most extreme severity – severe. In this case, the subject will be counted under the severe category.

7.2.1.4 TEAEs by Relationship

TEAEs will also be summarized by relationship to study drug, as assessed by the investigator, by the two treatment groups in Part 1 and by the four treatment groups in Part 2. If a subject has a TEAE with an unknown relationship, then the subject will be counted in the relationship category of "unknown," even if the subject has another occurrence of the same event with a relationship present. The only exception is if the subject has another occurrence of the same TEAE with a relationship assessment of "reasonable possibility." In this case, the subject will be counted under the "reasonable possibility" category.

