
Objectives (Continued): Exploratory Objectives (Continued)
 
• To assess the pharmacokinetic and immunogenicity of adalimumab with and without concomitant MTX.• To investigate various biomarkers and their associations with treatment responses and outcomes.

Investigators: Multi-center

Study Sites: Approximately 60 sites

Study Population: Approximately 240 adult subjects with active PsA (defined as not in MDA and having at least 3 tender and 3 swollen joints) despite having been treated with the first course of MTX at the dose of 15 mg ew for ≥ 4 weeks and biologic naive who meet all the inclusion and none of the exclusion criteria are planned to be enrolled in the study.

Number of Subjects to be Enrolled: 240 subjects in total, 120 subjects per randomized arm.

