6.1.3 Relationship to Study Drug

Assessment of adverse event relationship to the study medications(s) will be made with respect to adalimumab and MTX. The investigator will use the following definitions to assess the relationship of the adverse event to the use of study drug:

Reasonable Possibility	An adverse event where there is evidence to suggest a causal relationship between the study drug and the adverse event.
No Reasonable Possibility	An adverse event where there is no evidence to suggest a causal relationship between the study drug and the adverse event.

For causality assessments, events assessed as having a reasonable possibility of being related to the study drug will be considered "associated." Events assessed as having no reasonable possibility of being related to study drug will be considered "not associated." In addition, when the investigator has not reported a causality or deemed it not assessable, AbbVie will consider the event associated.

If an investigator's opinion of no reasonable possibility of being related to study drug is given, another cause of event must be provided by the investigator for the serious adverse event.

[figure not shown]

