8.1.5 Statistical Analyses of Safety

Safety analyses will be carried out using safety population, which includes all subjects that received at least one dose of study medication. Treatment-emergent AEs will be summarized and reported.

Treatment-emergent AEs are defined as AEs that begin either on or after the first dose of the study medication, and up to within 70 days after the last dose of the study medication. All treatment emergent AEs will be coded using the Medical Dictionary for Drug Regulatory Activities (MedDRA[®]). The number and percent of subjects experiencing AEs will be tabulated by system organ class and preferred term. In addition, a summary of AEs by severity and relationship to study drug will be presented. AEs, which are serious, severe, or life-threatening, which lead to premature study discontinuation will be listed and described in detail. Adverse event of special interest (AESI) will also be tabulated.

Observed values of vital signs and laboratory variables at each visit will be summarized for all treated subjects, and change from baseline in selected lab variables will be compared between treatment groups using a one way ANOVA. The last evaluation prior

to the first dose of study drug will be used as Baseline for the analyses in Part 1. For selected parameters, a listing of all subjects with any laboratory determination meeting Common Toxicity Criteria (CTC) (Version 3) of Grade 3 or higher will be provided. Shift tables for changes from Baseline according to the normal range will also be provided for laboratory variable.

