7.0 Safety Analyses

7.1 General Considerations

There will be 2 sets of safety analyses to be performed.

1. Safety analyses during Part 1 (up to Week 16).
2. Safety analyses during Part 2 (Week 16 to Week 32).

Safety analyses will include reporting of adverse events (AEs), laboratory, and vital signs measurements. Treatment-emergent AEs will be summarized and reported. Missing safety data will not be imputed. Part 1 and Part 2 safety analyses will be carried out using the Safety Population Part 1 and Safety Population Part 2, respectively.

Safety Analysis during Part 1 (up to Week 16)

Standard safety analysis by the "as treated" treatment groups of ADA 40 mg eow + MTX 15 mg ew and MTX 20 - 25 mg or highest tolerable dose ew will be performed on safety data up to Week 16. No protocol-defined treatment switching will occur prior to this time point.

Frequency tables of subjects with treatment-emergent adverse events (TEAEs) by system organ class (SOC) and by preferred term (PT) as in the Medical Dictionary for Regulatory Activities (MedDRA) dictionary will be provided by as-treated treatment groups.

Observed values in all continuous laboratory parameters and vital signs variables at each visit will be summarized by "as treated" treatment groups. Frequency tables of subjects meeting criteria for potentially clinically significant vital sign values and for potentially clinically significant laboratory values will be provided by as-treated treatment groups. Missing safety data will not be imputed.

Safety Analysis during Part 2 (Week 16 to Week 32)

Similar standard safety analysis by the "as treated" treatment groups will be performed on safety data from Week 16 to Week 32 based on Safety Population Part 2.

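### Where causality is missing, the SAP's related-TEAE counts may be lower, and can never be higher, than under the protocol's convention

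*SAP*

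**What the plan says.** Protocol 6.1.3 gives the investigator two causality categories, reasonable possibility and no reasonable possibility. It then sets a default for events without a usable rating: "when the investigator has not reported a causality or deemed it not assessable, AbbVie will consider the event associated". Protocol 8.1.5 promises that "a summary of AEs by severity and relationship to study drug will be presented" and says nothing further about missing causality.

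SAP 7.2.1.4 states: "TEAEs will also be summarized by relationship to study drug, as assessed by the investigator". It adds a third category: "If a subject has a TEAE with an unknown relationship, then the subject will be counted in the relationship category of" unknown, even when another occurrence of the same event has a rating. There is one way out: "The only exception is if the subject has another occurrence of the same TEAE with a relationship assessment of" reasonable possibility, in which case the subject moves to that category.

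SAP 7.2.1.1 lists six overview rows. One is "TEAEs reasonably possibly related to study drug"; none is for unknown relationship. SAP 7.1 adds a general rule: "Missing safety data will not be imputed". The SAP does not refer to the default in Protocol 6.1.3 and does not say that its tables set it aside.

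**The concern.** The two documents classify the same event differently. Under the protocol convention an event with no causality rating is associated with study drug. Under the SAP the subject leaves the related category and is shown as unknown.

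The relationship table at least displays these subjects. The overview is the weaker place. It has a related row and no unknown row, so its reader can neither see nor add back anyone left out. If SAP 7.2.1.4 is carried over to that row, the related figure rests on a less conservative convention than the protocol describes, and nothing on the page shows it. What is at stake is how a safety summary is read. No hypothesis test in the study depends on it.

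**Working it through.** The documents state no figure on this point, so there is none to reproduce. The check has two parts.

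**1. Where the two rules differ.** Take one subject and one preferred term. Let R be an occurrence rated reasonable possibility, N one rated no reasonable possibility, and U one with unknown relationship. SAP rule (7.2.1.4): related if any R; otherwise unknown if any U; otherwise not related. Protocol convention (6.1.3): related if any R or any U; otherwise not related.

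| Occurrences | SAP | Protocol convention |
|---|---|---|
| R | related | related |
| N | not related | not related |
| U | unknown | related |
| R, N | related | related |
| R, U | related | related |
| N, U | unknown | related |
| R, N, U | related | related |

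The rules differ in 2 of 7 combinations, U alone and N with U. In both, the SAP takes the subject out of the related category. In no combination does the SAP add one. The direction is therefore fixed: the SAP related count is less than or equal to the protocol-convention count.

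**2. How large the gap can be.** The denominator is the planned arm size in the Protocol synopsis, "240 subjects in total, 120 subjects per randomized arm". The number of affected subjects, u, is not in the documents, so the values below are assumed for illustration.

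Gap in percentage points = 100 × u / 120.

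| u (assumed) | Gap |
|---|---|
| 0 | 0 |
| 1 | 0.8 |
| 2 | 1.7 |
| 3 | 2.5 |
| 6 | 5.0 |

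Who counts towards u depends on the row. For a single preferred term, it is a subject with a U and no R for that term. For the overview it is a subject with a U and no R on any TEAE, because SAP 7.2.1.2 counts each subject once in the overall total. A subject with one unknown event and a different related event is already in the related overview row and adds nothing to the gap. So 0.8 points per subject with an unknown rating is an upper bound for the overview.

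Part 2 groups are smaller. If 20% of 120 MTX subjects reach MDA (the rate assumed in Protocol 8.2), the MTX responder arm has 0.20 × 120 = 24 subjects before dropout, and one affected subject is at most 1/24 = 4.2 points of that group. This shows how coarse the percentages are and is not evidence that any unknowns will occur.

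**The case against.** The strongest reply is that the two texts describe different assessors. The SAP table reports the investigator's view; the protocol sentence says how the sponsor will regard an event, in a section on recording and assessing adverse events. Protocol 8.1.5 does not say that the sponsor's convention governs the tables. Both rules can therefore operate together, and a reader who infers that the SAP breaks a protocol tabulation rule goes further than the text. This stands. What remains is that the protocol default applies exactly where there is no usable investigator rating, and the SAP does not say which convention its related row follows.

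Second, the SAP's choice looks deliberate. It does not impute missing safety data, it treats unknown severity in a similar way (7.2.1.3), and it ranks unknown above no reasonable possibility, so a missing rating is not hidden behind an unrelated one. This also stands for the relationship table, where unknowns are visible and can be added back. It does not cover the overview. Nor is the non-imputation rule applied strictly to adverse events: SAP 7.2.1 presumes that an event with an incomplete onset date is treatment-emergent unless there is evidence otherwise.

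Third, a reader might infer that the related counts are understated. The documents do not show that. Protocol 6.1 tells the investigator to record the relationship for any adverse event, and nothing indicates that ratings will be missing. The SAP does provide a rule for unknowns, so it allows for them. SAP 7.2.1.1 is also silent on how unknowns are classed. Silence leaves the row ambiguous; it does not exclude these subjects.

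**Conclusion.** The point holds as a minor inconsistency. The protocol convention and the SAP rule treat unreported or not assessable causality differently, and the SAP does not reconcile them. Related-TEAE counts may be lower than under the protocol convention, and never higher.

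For a given preferred term, the gap is the number of subjects with an unknown and no reasonable possibility rating for that term. For the overview, it is the number with an unknown and no reasonable possibility rating on any TEAE. In the overview each subject with an unknown rating is worth at most 0.8 points of a Part 1 arm, assuming the planned 120 per arm and that the overview follows the logic of SAP 7.2.1.4. The gap is zero if all causality fields are complete. The total cannot be stated, because the number of unknowns is not given.

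A reader might go on to conclude that the plan makes the study drugs look safer. That does not follow. It requires missing ratings that the documents do not show, and the relationship table shows any unknowns openly.

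**What to change.** - **SAP 7.2.1.1:** count TEAEs with missing or not assessable causality as related, in line with Protocol 6.1.3, and footnote the number of subjects so classified in each group.
- **SAP 7.2.1.4:** either apply the same classification, or keep the investigator-assessed unknown category and add a total for reasonable possibility plus unknown.
- **SAP 7.1:** state that this convention is an exception to the rule against imputing missing safety data, so that the two sections do not conflict.

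The cost is a few sentences of SAP text, one recode and one footnote or extra line. No new data are needed. The downside is that the related-AE figure may be slightly less favourable.
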